7.8 Follow-up phase assessments

- At Discharge:
 - Perform volume assessment by the Principal Investigator or a Sub-investigator who has been trained in the study volume assessment (Figure 3 in section 8)
 - Collect weight
 - Collect concomitant medication ([see Appendix 5](#))
 - Document length of hospitalization
 - Document and assess adverse events ([section 9](#))

- At Readmission:
 - HF readmissions are defined as either a hospital admission because of decompensated HF or an unscheduled contact at the emergency department if the patient is treated with intravenous loop diuretics.
 - During any readmission, EQ-5D questionnaire needs to be completed by the patient as soon as possible during the admission

- Long term follow-up

Patients will be followed for a maximum of three months for secondary/tertiary endpoint analysis. This follow-up should not differ from standard of care for such patients. During one outpatient follow-up appointment 3 months (90 days) (+ 14 days) after the start of study medication, standard of care data will be collected. The only study related tests will be a BNP / NT-ProBNP test and the collection of the EQ-5D patient questionnaire.

During this follow –up visit the following data will need to be collected:

- Collect vital signs including body weight, arterial blood pressure, heart rate
- EQ-5D patient questionnaire to be completed by the patient ([Appendix 2 and 3](#))
- Perform volume assessment by Principal Investigator or Sub-investigator who has been trained in the study volume assessment (Figure 3 in section 8)
- Collect blood sample for local laboratory assessment: serum hemoglobin, hematocrit, electrolytes (Na, K, Cl, HCO₃), serum urea, serum Cr, serum albumin, and plasma BNP or NT-proBNP. In a subset of randomized patients participating in the laboratory sub-study blood collected on this visit will be shipped to the University Biobank Limburg ([see section 7.10](#))
- Collect concomitant medication ([see Appendix 5](#))
- Document and assess adverse events ([section 9](#))

We do not foresee that a significant amount of patients will be lost to follow-up as the follow-up period is short (max 3 months). The investigator should make every effort to contact participants who are lost to follow-up. Attempts to contact such participants must be documented in the participant's records.

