7.11 Withdrawal criteria

All subjects will be encouraged to remain on treatment and under observation for the full duration of the study. However, at any time during the study and without giving reasons, subjects may withdraw from the study at their own request or at the request of their legally acceptable representative. The subject will not suffer any disadvantage as a result.

It is important to note that discontinuation of study treatment (see section 8) is not the equivalent to withdrawal of informed consent. In cases where subjects indicate they do not want to "continue", investigators must determine whether this refers to discontinuation of study treatment (the most common expected scenario), unwillingness to attend the follow-up visit, unwillingness to have telephone contact, unwillingness to have any contact with study personnel, or unwillingness to allow contact with a third party (e.g., family member, doctor). Every effort must be made to continue to follow the subject until the end of the study.

In all cases, the reason for discontinuation (including "at the subject's request") must be recorded in the case report form (CRF) and in the subject's medical records.

No subject replacements are permitted in the study.

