4.1.3 Secondary objectives and endpoints

Secondary Objectives	Secondary Endpoints

To investigate if combination therapy with acetazolamide:
 
 - leads to improved clinical outcome in decompensated HF (less HF readmissions, lower all-cause mortality) - shortens the length of stay in patients with decompensated HF, which is expected to reduce health care expenditure - leads to improved quality of life 	
 - Combined endpoint of all-cause mortality and HF readmission during 3 months of follow-up - Length of index hospital admission - Change in EuroQoL

Definition of secondary endpoints

- The combined endpoint of all-cause mortality and HF readmission during 3 months of follow-up is a binary endpoint. The time to the combined endpoint will be calculated as the time between start of study medication (day 1) and the date of (first) HF readmission or mortality (whichever comes first). *HF readmission* is defined as either a hospital admission or an unscheduled contact at the emergency department and when

treatment with intravenous loop diuretics is initiated because of worsening HF.

- Length of index hospital admission (calculated in days) is obtained as the date of discharge from the hospital minus the date of screening +1.
- EuroQol is a five dimension patient-reported QoL questionnaire (EQ-5D-5L). The EQ-5D-5L health states, defined by the EQ-5D-5L descriptive system, are converted into a single index value (<https://kce.fgov.be/nl/een-belgische-waardenset-voor-de-eq-5d-5l-%E2%80%93-hoe-gezondheidsgerelateerde-levenskwaliteit-waarderen>). The VAS assessment of the EQ-5D will also be used. The EQ VAS records the patient's self-rated health on a vertical visual analogue scale.

The index values and EQ-VAS at baseline, the morning of day 4 or discharge (whatever comes first), and at 3 months of follow-up will be used for the secondary objective.

During the study the baseline EQ-5D-5L questionnaire has been completed as soon as possible after screening up to day 1.

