4.5 Sample Size

The ADVOR study is powered for primary endpoint which is the most relevant endpoint with respect to the study hypothesis and reliable data from large randomized clinical trials are available to make a formal power calculation.

In the DOSE trial, which recruited a similar study population as targeted in the ADVOR study, successful decongestion with a similar definition was approximately 11% vs 18% after 72 h in the low vs high-dose loop diuretics arm. The high-dose loop diuretics arm of the DOSE trial is quite comparable to the standard of care group in the ADVOR study as the loop diuretic dose used in the latter is only slightly lower (2x instead of 2.5x the oral maintenance outpatient dose) and non-loop diuretics, which were infrequently used in the DOSE trial, are not allowed. Because of these slight differences, 15% is chosen as an estimate for occurrence of the primary endpoint in the monotherapy with high-dose loop diuretics (SOC) group.

No reliable data are available from large clinical trials to estimate occurrence of the primary endpoint in the acetazolamide arm of the ADVOR study. Therefore, after thorough discussion with the advisory board a success rate of 25% was chosen, which represents a clear meaningful benefit of 10% more patients with appropriate decongestion after 72 h. Using both estimates, considering a type I error rate $\alpha=0.05$ and type II error rate $\beta=0.20$ (yielding a statistical power of 80%), the targeted sample size for the ADVOR study is calculated at $n = 494$. A 5% drop out has been calculated in order to estimate the total number of 519 patients to be enrolled in the study.

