- To investigate the treatment effect on the time until combined endpoint of all-cause mortality and HF readmission during 3 months of follow-up a survival analysis will be performed. Time to event is defined as the time between day 1 and the date of (first) HF readmission or death if there was no HF readmission. The analysis will be censored at 3 months of follow-up or at the time when the patient was last known to be alive (for patients that withdraw or are lost to follow up), whichever occurs earlier. Survival times will be summarised descriptively using Kaplan-Meier survival curves. Formal testing for a difference in time to event will be done using a mixed-effect Cox proportional hazard model including the treatment arm and a random centre effect (ie, using a shared frailty model). The proportional hazards assumption will be verified by plotting log cumulative hazard versus log-time for the intervention and SOC group. Model validity will be further explored using plots of Cox-Snell and Martingale residuals. The treatment effect will be summarised as the hazard ratio (HR), 95% CI and associated p value.

To assess whether the treatment effect differs according subgroups defined on the basis of LVEF (see table in section 5.10.2) a subgroup analysis will be performed. The statistical model formulated for the analysis of this endpoints (binary and time to event version) will be extended to include a fixed effect for the subgroup and an interaction term between the study arm and the subgroup. The interaction term will be considered significant at the 5% level. Within each subgroup, summary statistics of the outcome by treatment arm will be presented; the OR/HR for the treatment effect and 95% confidence interval. A p-value for the interaction test will also be reported.

5.11.2 Secondary outcome 2

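### The time-to-event analysis of death or HF readmission censors lost patients at the date last known alive, so time with unknown readmission status can count as event-free (wrong as written, minor impact)

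*Combined protocol and SAP*

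**What the plan says.** SAP v2.0 section 5.11.1 analyses the "combined endpoint of all-cause mortality and HF readmission during 3 months of follow-up" in two ways: a binary mixed model and a survival analysis (Kaplan-Meier curves and a Cox model with a random centre effect). For the survival analysis, time to event is "the time between day 1 and the date of (first) HF readmission or death if there was no HF readmission". Follow-up is cut at 3 months or, if earlier, "at the time when the patient was last known to be alive (for patients that withdraw or are lost to follow up"). SAP v1.0 has the same rule. Protocol v2.0 section 10.3 names the Kaplan-Meier and Cox analyses but gives no censoring rule.

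SAP section 4.1.3 says that HF readmission "is defined as either a hospital admission or an unscheduled contact at the emergency department and when" intravenous loop diuretics are started for worsening HF.

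On loss, protocol section 7.8 says: "We do not foresee that a significant amount of patients will be lost to follow-up". Section 7.11 asks sites to establish which kind of follow-up a patient refuses. It lists "unwillingness to attend the follow-up visit, unwillingness to have telephone contact", and also "unwillingness to have any contact with study personnel, or unwillingness to allow contact with a third party". It asks that every effort be made to keep following the patient.

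**The concern.** The censoring date follows one half of the composite. Last known alive is the natural censoring date for death alone. For death or HF readmission, a patient can be counted as at risk and event-free only while both are known.

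The two dates can separate. Section 7.11 of the protocol recognises partial refusal, so a site may learn that a patient is alive without obtaining a readmission history. An emergency contact with intravenous diuretics at another hospital is easily missed in that situation. Under the stated rule such a patient stays in the denominator up to the last-alive date, although a readmission in that interval could not be seen.

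At stake are the Kaplan-Meier risks, which err low in any arm with such patients, and the hazard ratio, which is distorted if the arms have different numbers of them. No other planned analysis would reveal this. Multiple imputation (SAP 5.10.3) and the COVID-19 sensitivity analysis (5.10.4) are for the primary endpoint only.

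**Working it through.** **The plan's own figures.** The documents state no event rate, hazard ratio, loss rate or power for this analysis, so there is nothing to reproduce. The only loss figure is the sample-size allowance in SAP section 4.5: "A 5% drop out has been calculated in order to estimate the total number of 519 patients to be enrolled in the study". It follows from 494 × 1.05 = 518.7, rounded to 519, and 5% of 519 is about 26 patients. It belongs to the primary endpoint, which is settled by the morning of day 4, and does not forecast 3-month loss.

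**Assumptions (none from the documents).** Exponential event times over 90 days; 3-month control risk p of 20%, 30% or 40%; true hazard ratio 0.75; 259 patients per arm; a share L of each arm lost, with readmission status last known on day a = 30 or day 4 and the patient last known alive on day 90. These are long gaps. Every event after day a in a lost patient is taken to be unseen, which is towards the unfavourable end because deaths would usually be learned of.

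**Effect on the Kaplan-Meier risk.** Under the SAP rule, lost patients who are event-free at day a stay in the risk set to day 90 with no observable event. The estimated risk tends to

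(1 − L)·p + L·p_a, where p_a = 1 − (1 − p)^(a/90),

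so the shortfall is L·(p − p_a). With L = 5% in each arm:

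| p | a (day) | p_a | Risk under SAP rule | Shortfall (points) |
|---|---|---|---|---|
| 20% | 30 | 7.2% | 19.4% | 0.64 |
| 20% | 4 | 1.0% | 19.1% | 0.95 |
| 30% | 30 | 11.2% | 29.1% | 0.94 |
| 30% | 4 | 1.6% | 28.6% | 1.42 |
| 40% | 30 | 15.7% | 38.8% | 1.22 |
| 40% | 4 | 2.2% | 38.1% | 1.89 |

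Example, first row: 0.95 × 0.20 + 0.05 × 0.0717 = 0.1936. A simulation of 2,000 trials per scenario agrees (0.1936 for that row; 0.381 for the last). Censoring at day a instead recovers 20%, 30% and 40%.

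**Effect on the hazard ratio.** From the same simulation, using Cox without the centre effect:

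| Loss, control / acetazolamide | Censored at day a | SAP rule |
|---|---|---|
| 5% / 5% | 0.740 to 0.751 | 0.741 to 0.754 |
| 2% / 8% | 0.744 to 0.751 | 0.697 to 0.718 |
| 8% / 2% | 0.743 to 0.750 | 0.775 to 0.805 |

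With equal loss the hazard ratio hardly changes. With unequal loss it shifts by about 0.03 to 0.06, in favour of whichever arm loses more patients.

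**Scale against sampling error.** Risk in the acetazolamide arm is 1 − (1 − p)^0.75. At p = 20% this is 15.4%, giving 259 × (0.200 + 0.154) ≈ 92 events and a standard error of the log hazard ratio of about 2/√92 ≈ 0.21. At p = 40% it is 31.8%, giving about 186 events and a standard error of about 0.15. On the log scale the unequal-loss shifts run from 0.041 (0.746 to 0.716) to 0.076 (0.746 to 0.805), or roughly 0.2 to 0.5 standard errors.

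**The case against.** The strongest reply is that the gap is assumed. The documents describe no separate route to vital status, such as a registry or a closing sweep. Follow-up is one visit at 3 months plus attempts at contact, and deaths, HF rehospitalisations and serious adverse events are collected over the same period (protocol sections 7.8 and 9.2). A contact that shows the patient to be alive will often cover readmission too. The two dates then coincide and the rule does no harm. This stands: a gap is possible under section 7.11 but is not shown. It does not repair the rule, because nothing in either document requires readmission status to be known up to the last-alive date.

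The analysis also carries limited weight. SAP section 5.3 treats all non-primary endpoints as exploratory. The binary model, which gates the component analyses, does not use this censoring date. That stands as well, although section 5.11.1 still plans a formal test, a hazard ratio and a p value, and protocol section 3.3 calls the combined endpoint key.

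A reader might go further and infer that the event rates will be understated by a known amount because the plan itself expects 5% loss, or that the hazard ratio is biased in a fixed direction. The documents support neither. The 5% is the sample-size allowance, and protocol section 7.8 expects little loss. Nothing points to different loss by arm in a double-blind trial with study drug scheduled on days 1 to 3. Only the absolute risk errs in one direction; the hazard ratio can move either way.

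**Conclusion.** Wrong as written, minor impact. The censoring rule does not match the endpoint, and whenever vital status outlasts readmission information it counts unobserved time as event-free. That much follows from the text alone.

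The size rests wholly on assumptions and is likely to be small. The shortfall of 0.6 to 1.9 percentage points in 3-month risk needs 5% loss per arm and long gaps. The hazard-ratio shift of 0.03 to 0.06 also needs a 2% versus 8% imbalance, for which the documents give no ground. With equal loss the hazard ratio is essentially unaffected, and with coinciding dates nothing changes. The primary endpoint and the binary analysis of this endpoint are untouched.

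**What to change.** In SAP section 5.11.1, replace the censoring date for withdrawn or lost patients. Censor at 3 months or at the last date on which the patient was known to be both alive and free of HF readmission, whichever is earlier.

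Add one sentence, fixed before unblinding, on deaths learned of after that date. Counting them as events while censoring the comparable survivors earlier would push the risk up; ignoring them discards known events. One workable choice is to leave them out of the main time-to-event analysis and count them as events in a sensitivity analysis.

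No separate last-known-alive rule is needed for the mortality component unless a time-to-event mortality analysis is added, because section 5.11.1 analyses the components with the binary model.

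The cost is two sentences in the SAP and no new data collection, provided the date of the last readmission information can be derived from the recorded contacts. If only one contact date exists per patient, the new wording leaves the result unchanged.

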5.12 Analysis of safety outcomes

For the safety endpoints, all patients that were randomized and received at least 1 dose of the investigated drug or placebo will be included. For the safety analysis, patients will be grouped based on the actual study treatment received.

The safety outcomes are all binary outcomes. For descriptive purposes, the number (%) of failure and success for each safety outcome will be given per treatment arm.

For each safety outcome, the treatment effect will be evaluated by means of a generalized linear mixed model (logistic model). The statistical model will include a fixed treatment effect, and a random centre effect. The results of this model will be presented as an odds-ratio (OR), 95% confidence interval and the associated p value.

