
Exploratory tertiary end-points
	
 • Body weight change after day 1, 2, 3, 4 and discharge compared to screening • All-cause mortality during first 3 months after study start dose • Heart failure readmissions during first 3 months after study start dose • All cause rehospitalisations during first 3 months after study start dose • Total urinary volume and natriuresis starting from first intravenous (IV) diuretic administration at randomization until the morning of day 3 (urinary output, see figure 1 and appendix 4) • Relative plasma BNP or NT-proBNP change from screening until the assessment on day 4 or at discharge (whatever comes first) and at 3 months • Total dose of IV loop diuretics used during treatment phase. • Changes in doses of neurohumoral blockers from baseline to discharge and after 3 months • Need for renal replacement therapy or ultrafiltration during first 3 months after study start dose • Incidence of hyponatremia during treatment phase • Hypokalaemia during treatment phase • Incidence of metabolic acidosis requiring NaHCO₃ supplements during first 4 days • WRF defined as a >0.3 mg/dL increase in serum Cr, or a >20% decrease in eGFR by the CKD-EPI formula during treatment phase • Liver dysfunction at screening • Plasma volume changes during treatment phase (assessed by albumin and hematocrit) • Occurrence of iron deficiency at screening

	
Optional laboratory sub-study in participating centers:
 
 • Change from baseline in selected biomarkers from baseline through 3 months after study start dose in a subset of randomized patients
Safety assessments	
 • Adverse events • Laboratory values (including monitoring hypokalaemia, metabolic acidosis, substantial increase in creatinine (Cr), substantial decrease in eGFR)

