1 BACKGROUND

Aging of the population and prolongation of the lifespan of cardiac patients by modern therapeutic innovations have led to an increased incidence of HF (1). During the last two decades, important progress has been made in the treatment of ambulatory HFrEF patients. Renin-angiotensin system blockers, β -blockers, mineralocorticoid receptor antagonists, ivabradine, neprilysin inhibition, and cardiac resynchronization therapy have all been demonstrated to reduce morbidity and/or mortality in ambulatory HFrEF patients (2-18).

Despite these important advances, many patients are still hospitalized frequently with decompensated HF demonstrating most often signs and symptoms of systemic congestion and volume overload, which is associated with worse outcome (19). Treatment in these cases mainly focuses on symptomatic relief through administration of diuretics, although clear evidence on the optimal agent, dosing schedule, and administration route is lacking. Coexisting renal dysfunction often complicates decongestive treatment and worsening renal function (WRF), often defined as a 0.3 mg/dL rise in serum Cr, is a common finding in this context (20). However, the prognostic impact of WRF defined as Cr change is unsure as it might be associated with worse, neutral or even better outcome (21-23). In contrast, persistent congestion and volume overload, as a reflection of the renal inability to preserve sodium homeostasis, has been more consistently associated with higher mortality and more frequent readmissions in HF (24). This suggests that achieving a net negative fluid balance might be an attractive treatment target in decompensated HF.

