3.6 Exploratory tertiary endpoints

1. Body weight change after day 1, 2, 3, 4 and discharge compared to screening
2. All-cause mortality during first 3 months after study start dose
3. Heart failure readmissions during first 3 months after study start dose
4. All cause rehospitalisation during first 3 months after study start dose
5. Total urinary volume and natriuresis starting from first intravenous (IV) diuretic administration at randomization until the morning of day 3
6. Relative plasma BNP or NT-proBNP change from screening until day 4 or at discharge (whatever comes first) and at 3 months follow up visit
7. Total dose of IV loop diuretics used during first 4 days
8. Changes in doses of neurohumoral blockers from baseline to discharge and after 3 months.
9. Need for renal replacement therapy or ultrafiltration during first 3 months after study start dose
10. Hyponatremia during treatment phase
11. Hypokalaemia during treatment phase
12. Incidence of metabolic acidosis requiring NaHCO₃ supplements during first 4 days
13. WRF defined as a >0.3 mg/dL increase in serum Cr, or a >20% decrease in eGFR by the CKD-EPI formula during treatment phase
14. Liver dysfunction at screening
15. plasma volume changes during treatment phase (assessed by albumin and hematocrit)
16. Occurrence of iron deficiency at screening
17. Optional laboratory sub-study in participating centers: Change from screening in selected biomarkers from baseline through 3 months after study start dose in a subset of randomized patients

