10.3 Statistical analysis plan

- The treatment effect for the primary end-point [Treatment success (decongestion achieved) on the morning of day 4 without escalating diuretic strategy (doubling loop diuretic dose, addition of chlorthalidone, or ultrafiltration) during IV diuretic therapy on morning of day 3 is evaluated by means

of a generalized linear mixed model. The statistical model will include a fixed treatment effect and random center effect.

- For the first secondary end-point [occurrence of the combined endpoint of all-cause mortality and heart failure readmission during 3 months of follow-up], a generalized linear mixed model for a binary outcome will be used. The model will incorporate a fixed treatment effect and random center effect. If the treatment effect on the composite endpoint of 'all-cause mortality and HF readmission' turns out to be statistically significant, both components will be evaluated separately in a hierarchical fashion with HF readmissions first and all-cause mortality second. For this analysis, HF readmission will include patient dying from HF during the 3 months of FU. As a sensitivity analysis the worst case scenario, assuming a HF readmission for all patients dying to non HF related causes during the 3 month follow-up will be executed.
- Length of index hospitalization and change in quality of life scores are compared among treatment arms with a linear mixed model (fixed treatment effect and random center effect). Transformation will be employed when the model assumptions (such normality) are violated.
- All hypothesis are 2-sided and tested with a significance level of $\alpha=0.05$.

The proposed statistical models all assume the missing data mechanism to be missing at random. To investigate the sensitivity of the conclusions with respect to this assumption, a sensitivity analysis by means of multiple imputation technique will be performed.

Secondary Analysis:

- All statistical models discussed in the secondary analysis include a fixed treatment effect and random effect for the center, and in case of longitudinal outcome random patient effects (intercept, slope).
- The mixed models for the primary and secondary end-point analyses will be extended with explanatory variables (such as gender, age, race, ethnicity, kidney function, neurohumoral blockers, diuretics and blood pressure)
- For the end-points collected repeatedly over time, the rate of change will be investigated using longitudinal data models.

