4.1.4 Safety objectives and endpoints

Safety Objective	Safety Endpoints
To evaluate the safety of the combination therapy with acetazolamide in this patient population.	
 - Severe metabolic acidosis at any time during study treatment - Doubling or more ($\geq 2x$) of baseline serum Creatinine, or $\geq 50\%$ decrease in baseline eGFR at any time during study treatment - Hypokalaemia at any time during study treatment - Hypotension at any time during study treatment

Definition of Safety endpoints

- Severe metabolic acidosis: a value of bicarbonate < 12 mmol/L at any time during study treatment (day 1- day 4)
- Worsening of eGFR or the need for renal replacement therapy during the index hospitalization. eGFR is obtained via the CKD-EPI formula. The eGFR values will be calculated (in mL/min/1.73 m²) from the local laboratory creatinine measurements using the CKD-EPI formula (Levey et al 2009)².
- Hypokalaemia: a value of potassium $\leq 3,0$ mmol/L at any time during study treatment (day 1- day 4)
- Hypotension: a value of systolic blood pressure < 85 mmHg at any time during study treatment (day 1- day 4)

Baseline laboratory value

For all laboratory variables, the baseline value is defined as the last value prior to the first dose of study drug.

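### SAP v2.0 keeps only strict binary cut-offs for acidosis and renal function and no longer lists protocol tertiary endpoints 12 and 13; restoring them and adding one bicarbonate model is a cheap improvement

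*Combined protocol and SAP*

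**What the plan says.** Protocol v2.0 section 3.6 lists as tertiary endpoint 12 "Incidence of metabolic acidosis requiring NaHCO₃ supplements during first 4 days" and as endpoint 13 "WRF defined as a >0.3 mg/dL increase in serum Cr, or a >20% decrease in eGFR by the CKD-EPI formula during treatment phase". The safety assessments in the protocol's trial summary name metabolic acidosis, a substantial creatinine rise and a substantial eGFR fall.

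SAP v2.0 section 4.1.4 sets four safety endpoints. The acidosis one is "Severe metabolic acidosis: a value of bicarbonate < 12 mmol/L at any time during study treatment". The renal one is at least a doubling of creatinine or at least a 50% fall in eGFR; the definition beneath the table adds "Worsening of eGFR or the need for renal replacement therapy during the index hospitalization". The other two are potassium of 3.0 mmol/L or less and systolic pressure below 85 mmHg. Section 5.12 says "The safety outcomes are all binary outcomes" and analyses each with a logistic mixed model (fixed treatment, random centre).

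The exploratory list in SAP 4.1.5 has 13 entries. Hyponatraemia (protocol item 10) is there; items 12 and 13 are not. The SAP document history gives no reason for this. No SAP section analyses bicarbonate or creatinine as a continuous value.

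**The concern.** The safety cut-offs lie beyond the levels at which the plan itself acts. NaHCO3 is recommended below 20 mmol/L (SAP 4.3.3), and study treatment may be stopped at 1.5 times the admission creatinine (SAP 4.3.1). The safety outcomes start at 12 mmol/L and at twice the baseline creatinine. A patient with a bicarbonate of 15 mmol/L, for whom treatment is recommended, is recorded as having no acidosis event.

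Acetazolamide is a carbonic anhydrase inhibitor, and the protocol names metabolic acidosis for laboratory monitoring. The stated safety objective is to evaluate the combination in this population. If the drug lowers bicarbonate moderately, the listed analyses may show nothing, and the reader cannot tell whether items 12 and 13 will be reported.

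**Working it through.** **Comparison of the lists.** Protocol items 11 (hypokalaemia), 12 (acidosis) and 13 (WRF) all have a counterpart in SAP 4.1.4. For 12 and 13 the counterpart is a stricter outcome: below 12 mmol/L in place of acidosis needing NaHCO3, and doubling or halving in place of a rise above 0.3 mg/dL or a fall above 20%. The protocol versions appear nowhere in SAP 4.1.4 or 4.1.5.

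**Figures.** The plan gives no figure on this point to reproduce. From the documents: 519 patients at 1:1 is 519/2 = 259.5, so about 260 per arm; two-sided 5% level; morning samples on days 2, 3 and 4 (protocol 7.7.2). Assumed, because the documents give no laboratory means, SDs or drug effects: bicarbonate normal with mean m = 25 mmol/L, SD s = 3, 4 or 5, correlation 0.7 between mornings and 0.6 with baseline, and a constant fall on drug.

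*Binary outcomes.* The probability of at least one of three mornings below cut-off c is

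p = 1 − ∫ φ(u) [1 − Φ((c − m − s√0.7·u)/(s√0.3))]³ du.

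Power is the exact two-sided Fisher test at 260 per arm. The chance that at least one arm has no events, so that the odds ratio has no finite estimate, is 1 − [1 − (1−p0)^260][1 − (1−p1)^260].

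*Adjusted mean.* The variance per patient of the three-morning average is s²[(1 + 2×0.7)/3 − 0.6²] = 0.44s². The SE is s√(2×0.44/260) = 0.058s, that is 0.17, 0.23 and 0.29. The 95% half-width is 1.96 × SE = 0.34, 0.46 and 0.57 mmol/L.

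Results for a fall of 2 mmol/L:

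| | SD 3 | SD 4 | SD 5 |
|---|---|---|---|
| Below 12: expected events, placebo vs drug | 0.01 vs 0.1 | 0.4 vs 1.9 | 2.9 vs 8.2 |
| Below 12: power | 0% | 1% | 25% |
| Below 12: an arm with no events | >99% | 72% | 5% |
| Below 20: expected events | 26 vs 73 | 52 vs 98 | 73 vs 115 |
| Below 20: power | >99% | 99% | 96% |
| Adjusted mean: power | >99% | >99% | >99% |

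**Sensitivity.**
- Larger falls, power for below 12 at SD 3/4/5: fall of 3, 0/14/67%; fall of 4, 0/63/96%.
- Baseline mean 23 to 27, fall of 2: below 12, 0 to 56%; below 20, 92% to >99%.
- If supplements halve the mean difference to 1 mmol/L, the adjusted mean keeps 93% at SD 5 (1/0.29 = 3.44; Φ(3.44 − 1.96) = 93%).
- Item 12 itself: 61 to 94% if half of those below 20 receive NaHCO3; 37 to 74% if 30% do.
- Day 2 alone (variance s²(1 − 0.6²) = 0.64s²): >99% for a fall of 2, 81% to >99% for 1, and 30 to 66% for 0.5.
- Cruder version with one measurement, mean 24 or 26, 259 per arm and a normal approximation: below 12, 3 to 27%; below 20, 85% to >99%; mean, at least 99%.

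**Renal counterpart.** Assumptions: SD of log creatinine change 0.15 to 0.25, eGFR proportional to creatinine to the power −1 to −1.2, mean rise 10%. Doubling or halving has 0 to 43% power. With renal replacement at 1 to 2% in both arms it is 1 to 35%, and 7 to 60% if replacement also doubles. The eGFR part of item 13 (a fall above 20%) has 95% to >99%. For a 5% rise the contrast is 0 to 10% against 42 to 80%.

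**The case against.** Several points on the other side carry weight.

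*Redefinition rather than neglect.* Items 11 to 13 are the three whose domains reappear in the SAP safety section, with a named model, which is more than any exploratory endpoint gets. That looks like a deliberate move to serious thresholds. A reader might infer an accidental or selective omission; the documents support neither. What stands is that the milder versions are no longer listed and no reason is recorded.

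*General rules.* Protocol 10.3 says "For the end-points collected repeatedly over time, the rate of change will be investigated using longitudinal data models", and SAP 5.1 promises an estimate and interval for each exploratory outcome. SAP 5.1 also limits the SAP's scope to primary and secondary objectives, and no exploratory endpoint has its own model. The rule in 5.1 can be read to reach items 12 and 13, because the protocol calls them exploratory. But they are off the SAP's own list, so this remains a matter of interpretation.

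*Adverse events.* Protocol 9.2 requires non-serious events involving potassium, sodium or bicarbonate to be recorded, so moderate disturbances are captured. The SAP names no analysis of them.

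*Creatinine.* Mean creatinine change was never an endpoint, and protocol section 1 says the "prognostic impact of WRF defined as Cr change is unsure as it might be associated with worse, neutral or even better outcome". A reader might infer that the SAP must model it. The documents do not support that, and a mean shift would be hard to read as harm.

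*Assumed inputs.* Power for below 12 runs from 0 to 96% over SD 3 to 5 and falls of 2 to 4 mmol/L, and the trial was not sized for safety. The contrast is illustrative.

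**Conclusion.** The point holds as a cheap improvement to the safety objective. Followed as written, the SAP no longer lists two protocol endpoints and relies on an acidosis measure that is insensitive to a moderate bicarbonate fall: about 0 to 25% power for 2 mmol/L, against 96% or more for below 20 and over 99% for the adjusted mean. This rests on the assumed mean of 25, SD of 3 to 5 and the stated correlations. For falls of 3 to 4 mmol/L at wider SDs, below 12 does gain power.

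A reader might infer that the planned safety results would mislead, or that the strict cut-offs should go. The documents do not support this. The four outcomes are a defensible measure of serious harm, a finding of no difference in severe acidosis could be correct, and the primary and secondary conclusions are untouched.

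**What to change.** Keep the four binary outcomes and add to SAP 5.12, labelled exploratory:

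1. Protocol items 12 and 13 by arm, with n (%), odds ratio and 95% CI from the same logistic mixed model. Add bicarbonate below 20 mmol/L on any morning as support for item 12, because NaHCO3 is only recommended and item 12 therefore partly measures prescribing. The full eCRF medication list is also not in the documents. Read WRF descriptively.
2. One repeated-measures model of day 2 to 4 bicarbonate in the safety population (day-4 value at discharge if earlier), with treatment, day, treatment-by-day, baseline value and random centre, reporting the difference and 95% CI for each morning. An unstructured within-patient covariance suits three mornings; it differs slightly from the random intercept and slope in SAP 5.11.3. State that values are kept after supplements, after stopping at decongestion and after day-3 escalation, so the estimate is the effect of the whole strategy.

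Models for continuous creatinine, potassium and systolic pressure are optional. If the sponsor prefers to leave items 12 and 13 out, the SAP should say so and why. Anything added after unblinding should be labelled post hoc.

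The cost is SAP wording, three binary analyses and one model, on samples already drawn each morning. The downside is a few more exploratory estimates without multiplicity control, which SAP 5.3 already accepts.
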